9.3.2 Outcomes

9.3.2.1 Primary outcomes

Outcome name: demographic and clinical characteristics of patients who had a prescription of OADs.

Time frame: on the index month

Safety issue: N/A

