9. RESEARCH METHODS

9.1 STUDY DESIGN

Study design:

- Descriptive cohort study

Comparison group

- OAD group, DPP-4 inhibitors group, SU group, BG group, TZD group, α -GI group, and Glinide group.

Strength of the study design

- Up-to-date information can be obtained and nationwide actual treatment status can be illustrated with using large-scale real-world database.

Analysis

- First analysis: type and dosage of drug prescribed for T2DM patients.
- [REDACTED]
- Main measures: number of patients, baseline characteristics at index month (age, sex), prior and concomitant use of glucose-lowering medications and insulin (type, dose), comorbidities (types and their percentages of patients), stage of RI defined by eGFR or serum creatinine value, glucose-lowering medications and their dosages (based on daily dose) for patients with RI, [REDACTED]
- [REDACTED]

Potential limitation

- The data held in MDV database is collected from DPC hospitals, not GP data. However they are including outpatient data because many of Japanese patients prefer to visit a hospital even though chronic disease.
- The rate of laboratory test data held in MDV database is limited. About 350,000 patients out of 2,600,000 patients (13.5%, April 2008 ~ April 2016) have laboratory data.
- The MDV database does not hold the time diagnosis of T2DM if it is out of study period. Therefore the onset date of diabetes or the first record of T2DM cannot obtain for all patients.
- The information on medication is based on prescribed record, not include adherence result. It means that exact dosage may not reveal actual dispensed prescription and dosage perfectly.
- Laboratory test date is not exactly matched with the index day of the first prescription of OAD. The sample size will have some impacts (reduction) to assure simultaneous timing of data. The latest lab result 30 days before the index date will be considered the status at the time of prescription
- All information of each patient is from consent given DPC hospitals. If patients have visits to other medical institutions, these data are not included in the MDV data.

- MDV database is composed of data from patients who hospitalized in DPC hospital so that more severe patient will be included in the database.

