9.2 SETTING

Medical Data Vision (MDV) clinical database is used.

Inclusion criteria

[figure not shown]
- Patients with T2DM (ICD code: E11 or E14).
- Patients must have their first prescription (defined as index date*) for any study drugs between 01/01/2014 and 30/09/2016.
- Patients must have at least 6 months enrolment verified by the presence of any record except for the study drug prescriptions within the database (look back period) prior to the index date for each drug.

Exclusion criteria

- Patients who were under 40 y.o. at the time of diagnosis of diabetes.
- Patients with record of type 1 diabetes mellitus (ICD code: E10).
- Patients who prescribed the study drugs during 6 month prior to index date for each drug.
- Patients whose mean visit interval are more than 92 days

*Index date is defined as follows:

- In case of comparing drugs within class, index date is defined as the date of first prescription for any study drugs as general name. Change of dosage is not counted as the index.
- In case of comparing drugs between class, index date is defined as the date of first prescription for study drug of class. Change of dosage is not counted as the index.

* The hospitalization period is not included in the mean visit interval.

Figure 1 Definition of Index data(date of first prescription for any study drugs)

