9.7 DATA ANALYSIS

9.7.1 Main analysis

- For the primary objective, descriptive statistics of patients prescribed each compound and each class of OAD at least once will be presented for the baseline demographic and clinical characteristics:
 - Number of patients (n, % of total patients)
 - Age (mean ± SE, mean ± SD)
 - Sex
 - Concomitant medications (drug prescribed at index day) :
 - Use of biguanide (Yes/No)
 - Use of sulfonylurea (Yes/No)
 - Use of thiazolidinediones (Yes/No)

- Use of glinide (Yes/No)
- Use of α -GI (Yes/No)
- Use of GLP-1RA (Yes/No)
- Use of SGLT2 inhibitors (Yes/No)
- Use of insulin (Yes/No)
- Premedications (drug prescribed before index day):
 - Use of biguanide (Yes/No)
 - Use of sulfonylurea (Yes/No)
 - Use of thiazolidinediones (Yes/No)
 - Use of glinide (Yes/No)
 - Use of α -GI (Yes/No)
 - Use of GLP-1RA (Yes/No)
 - Use of SGLT2 inhibitors (Yes/No)
 - Use of insulin (Yes/No)
- Comorbidities:
 - Hypertension: Percentage of patients with a diagnosis of hypertension
 - Ischemic heart disease (IHD): Percentage of patients with a diagnosis of IHD
 - Myocardial Infarction (MI): Percentage of patients with a diagnosis of MI
 - Heart Failure (HF): Percentage of patients with a diagnosis of HF
 - Stroke: Percentage of patients with a diagnosis of stroke
 - Renal impairment: Percentage of patients with a diagnosis of renal impairment
 - Amputation: Percentage of patients with a diagnosis of amputation

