11. MANAGEMENT AND REPORTING OF ADVERSE EVENTS/ADVERSE REACTIONS

The outcomes of the study are the baseline characteristics (pre-treatment) and medication prescriptions. We will not be looking at outcomes during the treatment period; therefore safety reporting is not applicable for this study.

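### Comorbidities have no window except the undefined index month, which leaves most of the required 6-month look-back unused and may admit diagnoses made after the first prescription

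*Combined protocol and SAP*

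**What the plan says.** Section 9.3.2.1 names the primary outcome: "Outcome name: demographic and clinical characteristics of patients who had a prescription of OADs". Its window is "Time frame: on the index month". No start day or end day is given, and nothing says whether a calendar month or a month counted from the index date is meant. Section 9.2 defines the index date only.

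Section 9.1 lists the main measures as "baseline characteristics at index month (age, sex), prior and concomitant use of glucose-lowering medications and insulin (type, dose), comorbidities". The index month is attached there to age and sex; comorbidities follow in the same list with no window.

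Other sections set windows for some components:

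- Age is taken at the index date (9.3.3).
- Drugs are tied to the index day in 9.7.1: "Concomitant medications (drug prescribed at index day". Premedication is what was prescribed before that day.
- Serum creatinine is the latest value within 6 months of the index date (9.3.3), or the latest result 30 days before it (9.1 and 9.9).

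Comorbidities get an ICD-10 definition in 9.3.3 and a percentage in 9.7.1, for example "Myocardial Infarction (MI): Percentage of patients with a diagnosis of MI". Neither place gives a period.

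Section 9.2 requires at least 6 months of enrolment before each index date and calls this the look-back period. It is an eligibility criterion. Section 11 states: "The outcomes of the study are the baseline characteristics (pre-treatment) and medication prescriptions". It adds: "We will not be looking at outcomes during the treatment period".

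**The concern.** The study is descriptive, and the comorbidity percentages by compound and class are a large part of its primary result. A percentage with a diagnosis has meaning only together with the period searched for that diagnosis.

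Read as written, 9.3.2.1 confines that search to about one month. MI, stroke and amputation are events. One coded three months before the first prescription would not be counted, although the design guarantees that the patient was already enrolled then. Renal impairment shows the mismatch within one condition: by diagnosis code it is sought in the index month, while by creatinine 9.3.3 allows 6 months.

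The undefined term also leaves open whether days after the first prescription count. If they do, the amount of time before and after index differs between patients only because of the day of the month on which they were indexed. Two programmers could produce different primary tables from this text, and the independent calculation check in section 9.8 would have no stated window to check against.

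**Working it through.** The protocol gives no figure to reproduce, so the check is a calendar count.

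**Inputs.** Index dates run from 01/01/2014 to 30/09/2016 (9.2). That is 33 months: 19 of 31 days, 11 of 30 days, two of 28 and one of 29, so 589 + 330 + 56 + 29 = 1,004 dates. The look-back is 6 months (9.2), which is 181 to 184 days depending on the date, on average 182.6. Assumption: every index date is equally likely.

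**Reading A: calendar month containing the index date.** For index day d in a month of L days, d − 1 days fall before index and L − d after it. Each sums to L(L − 1)/2 over a month.

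- Total: 19 × 465 + 11 × 435 + 2 × 378 + 406 = 14,782.
- Mean days after index: 14,782 / 1,004 = 14.7 (range 0 to 30). The mean number of days before index is the same.
- Dates with at least one later day in the month: (1,004 − 33) / 1,004 = 96.7%.
- Average share of the month after index: (971 / 2) / 1,004 = 48%.
- Share of the look-back used: on average 8.1% (about 14.7 / 182.6), at most 30 / 181 = 16.6%.

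**Reading B: 30 days ending at the index date.**

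- Days after index: 0.
- Share of the look-back used: 30 / 184 = 16.3% to 30 / 181 = 16.6%.

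**Comparison**

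| Window | Look-back used | Days after index |
|---|---|---|
| Calendar month | mean 8.1%, maximum 16.6% | mean 14.7, range 0 to 30 |
| 30 days ending at index | 16.3% to 16.6% | 0 |
| 6 months up to index | 100% | 0 |

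On both one-month readings at least 100 − 16.6 = 83.4% of the look-back is unused. Days after index arise only on reading A, or on another reading that runs past the index date.

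**The case against.** The strongest reply is that the index month is a loose header which the detailed sections override. They do so for age, drugs and creatinine, and 9.1 attaches the phrase only to age and sex. On this view the comorbidity window is unspecified, not limited to one month. Figure 1 is not shown and parts of the text are redacted, so a window may exist out of sight. This stands to a degree: the finding holds for the visible text. But no visible section overrides the header for comorbidities, and a programmer who follows the text has only the index month to apply.

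Second, a reader might infer that the plan counts drugs and diagnoses recorded after treatment start as baseline. The documents do not support that as a general statement. Section 9.7.1 fixes drugs to the index day or earlier, and age is taken at the index date. For diagnoses it depends on what the month means. The calendar month is the natural reading, since the protocol says so explicitly when it wants a backward window. Section 11, however, can be used to interpret the phrase the other way, as a month ending at index.

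Third, a reader might infer that leaving the look-back unused breaks a rule of the protocol. It does not, because the look-back serves eligibility and is never named as the comorbidity window. Using it is a design recommendation.

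Fourth, days are not diagnoses. Using 8% of the look-back days does not mean finding 8% of the comorbidities, since every patient has a prescription inside the window. This stands in full.

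**Conclusion.** The point holds for comorbidities. Their only visible window is an undefined month, and on either reading tested at least 83% of the 6-month look-back is unused, so events coded earlier in it can be missed. This part does not depend on how index dates are spread.

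Inclusion of post-prescription time is conditional. If the calendar month is meant, about 14.7 days on average would count as baseline, contrary to section 11. That average assumes evenly spread index dates.

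The effect on any percentage cannot be computed, because the documents give no rates at which diagnoses are recorded. On the calendar-month reading the two errors pull in opposite directions, so even the net direction is unknown. The change should be made because these percentages are the primary result, but nothing here shows that any of them would be materially wrong.

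**What to change.** For comorbidities, replace the index month in 9.3.2.1 with diagnoses recorded in the 6 months before and up to the index date, applied to each index date that 9.2 defines by drug or by class. State the same window in 9.3.3 and 9.7.1. Keep the existing index-date rule for age and index-day rules for drugs, and bring 9.1 and 9.3.2.1 into line with them, so that all of these agree with the pre-treatment statement in section 11.

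The cost is protocol wording and a date filter on data already held; no further data are needed. Section 6 plans the analysis for 1 to 10 March 2017, so the window should be settled before programming starts. Nothing in the documents says that diagnoses are dated only to the month. A rule for that case should be added only if the data prove to be so.

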9.3.2.2 Secondary outcomes

Outcome name: drug and dosage (based on daily dose) they are prescribed as there are different cut-offs for renal functions.

Time frame: on the index month

Safety issue: N/A

9.3.3 Covariates

Age at index date

Sex

Prior and concomitant use of glucose-lowering medications and insulin (type, dose): drug name was defined by ATC code and drug name.

Comorbidities (types and their percentages of patients): defined by ICD-10 code

Stage of RI: defined by eGFR or serum creatinine value (See [Annex 3](#)).

eGFR is calculated using serum creatinine, age, and sex as follows (formula for Japanese):

The latest serum creatinine value within 6 months from index date will be used.

*where Cr is serum creatinine (mg/dL), age is the age at index date.

- eGFR formula*:

$$\text{eGFR (mL/min/1.73m}^2\text{)} = 194 \times \text{Cr}^{-1.094} \times \text{age (year)}^{-0.287} (\times 0.739 \text{ if female})$$

*The formula recommended by the Japanese Society of Nephrology in clinical practice in Japan is the above formula calculated from three data of serum creatinine, age and sex.

<References>

- (Japanese) Evidence-based Clinical Practice Guideline for CKD 2013 (the Japanese Society of Nephrology)
URL (accessed on 1st Feb, 2017):
http://www.jsn.or.jp/guideline/pdf/CKD_evidence2013/all.pdf
- (English) Japanese Society of Nephrology. Clin Exp Nephrol 2014;18: 346.

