MDV provides commercial claims database for inpatient and outpatient consisting medical records from more than 12.94 million patients from 230 large acute care DPC hospitals as of Feb 2016. According to the data released by the company in Sept 2016 [1], in one year period between July 2015 and June 2016, cumulative number of patients in the claims database was 7,546,862 patients. 82% of patients (6,152,732) were associated with outpatient claims only, while 15% of patients (1,131,869) had claims from both in and out-patient care. Only 3% of patients (262,261) had exclusively in-patient claims. Laboratory data is available for approximately 10% of patients contained in the database. The DPC is a case-mix system, similar to Medicare in the US. It comprises of 18 Major Diagnosis Categories, 520 diagnostic groups and 2,658 case-mix groups. In the DPC algorithm, the diagnosis, procedure and comorbidities/complications are the 3 key variables for classification. The diagnosis and comorbidities/complications are coded using the ICD10 scheme, while the procedures are coded using the Japanese Procedure Codes. Not only administrative claims data but also

detailed patient data are collected for all the inpatients discharged from the participating hospitals.

[figure not shown]

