ANNEX 3. ADDITIONAL INFORMATION

1. Stage of renal function by eGFR

		eGFR (ml/min/1.73m ²)
G1	Normal or high	≥90
G2	Normal or mildly decreased	60-89
G3a	Mildly to moderately decreased	45-59
G3b	Moderately to severely decreased	30-44
G4	Severely decreased	15-29
G5	ESKD	<15

ESKD: End Stage Kidney Disease

2. Stage of renal function by serum creatinine value

	Serum Creatinine (Cr) (mg/dL)
Normal	Male: $0.6 < Cr \leq 1.2$ Female: $0.4 < Cr \leq 0.9$
Mild	Male: $1.2 < Cr \leq 1.4$ Femal: $0.9 < Cr \leq 1.2$
Moderate	Male: $1.4 < Cr \leq 2.4$ Female: $1.2 < Cr \leq 2.0$
Severe/ ESKD	Male: $Cr > 2.4$ Female: $Cr > 2.0$

APPROVAL / SIGNATURE PAGE**Document Number: c12992044****Technical Version Number:1.0****Document Name: nis_protocol_based_on_existing data_1218_0178**

Title: Clinical characteristics and practice patterns of Type 2 Diabetes Mellitus (T2D) patients treated with oral antidiabetic drugs (OAD) in Japan: analysis of medical and health care database of the Medical Data Vision (MDV)

Signatures (obtained electronically)

Meaning of Signature	Signed by	Date Signed
Approval-Clinical Program [REDACTED]	[REDACTED]	10 Feb 2017 01:46 CET
Approval-Medical [REDACTED]	[REDACTED]	10 Feb 2017 03:37 CET
Approval [REDACTED] Medical Affairs	[REDACTED]	10 Feb 2017 04:10 CET

(Continued) Signatures (obtained electronically)

Meaning of Signature	Signed by	Date Signed
-----------------------------	------------------	--------------------

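### Renal stage rests on one creatinine value with no dialysis rule in the readable text, so a dialysis patient with a low value may be staged as less severe than ESKD

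*Combined protocol and SAP*

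**What the plan says.** Section 9.3.3 gives the basis of staging as "Stage of RI: defined by eGFR or serum creatinine value". Both routes use the same laboratory result: "The latest serum creatinine value within 6 months from index date will be used". For the first route, "eGFR is calculated using serum creatinine, age, and sex as follows (formula for Japanese") is followed by the equation eGFR = 194 × Cr^-1.094 × age^-0.287, times 0.739 for women.

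Annex 3 holds two schemes. In the eGFR scheme, G4 is 15-29 and G5 is below 15; G5 carries the label ESKD, spelled out in the footnote as "ESKD: End Stage Kidney Disease". The other scheme, headed "Stage of renal function by serum creatinine value", has one merged class, Severe/ESKD, for Cr above 2.4 mg/dL in men and above 2.0 in women. Moderate runs from above 1.4 to 2.4 in men and from above 1.2 to 2.0 in women.

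The secondary outcome (9.3.2.2) is "drug and dosage (based on daily dose) they are prescribed as there are different cut-offs for renal functions". Section 7 says that diagnoses in the source are coded in ICD-10, "while the procedures are coded using the Japanese Procedure Codes". The main analysis (9.7.1) also lists "Renal impairment: Percentage of patients with a diagnosis of renal impairment", but nothing readable links that diagnosis to the stage. Dialysis is not mentioned in the readable text of the eligibility criteria, covariates, analysis, limitations or bias sections.

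**The concern.** A creatinine-based eGFR assumes that the blood level reflects clearance by the kidneys. In a dialysis patient it also reflects clearance by the machine and the time since the last session. A patient with end-stage disease by any definition can therefore have a recent creatinine that the formula converts to an eGFR of 15 or more. Nothing in the readable eligibility criteria (9.2) keeps such patients out, and nothing in 9.3.3 or Annex 3 overrides the formula for them. For these patients, the rule as written can return a wrong class.

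What is at stake is the axis of the secondary outcome. Section 7 says the study aims to describe dose selection in patients with renal impairment, and that several drug classes carry restrictions that depend on its severity. Dialysis patients placed in G4, or in Moderate in the second scheme, would mix their prescribing with that of patients with less advanced disease, and ESKD would be under-counted.

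**Working it through.** The plan states no figure on this point to reproduce. The check asks at what creatinine value the plan's own rules stop returning ESKD.

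**Inputs from the documents.** The eGFR formula (9.3.3); the G5/G4 cut-off at eGFR 15 and the G4/G3b cut-off at 30 (Annex 3); the Severe/ESKD limits of 2.4 and 2.0 mg/dL (Annex 3).

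**Inputs assumed.** Pre-dialysis creatinine of 5 to 12 mg/dL and a fall of 50 to 70% over a session. The documents give neither.

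**Step 1: creatinine at the G5 boundary.** Inverting the formula:

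Cr = (194 × age^-0.287 × [0.739 if female] / 15)^(1/1.094)

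At age 65, 194 × 65^-0.287 ≈ 58.5. For a man, (58.5/15)^(1/1.094) = 3.47. For a woman, (58.5 × 0.739/15)^(1/1.094) = 2.63.

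| Age | Man, Cr at eGFR 15 | Woman, Cr at eGFR 15 |
|---|---|---|
| 40 | 3.94 | 2.99 |
| 65 | 3.47 | 2.63 |
| 70 | 3.41 | 2.58 |
| 80 | 3.29 | 2.49 |

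At or below these values the patient is staged G4 or better. Above them the plan already returns G5.

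**Step 2: assumed values after a session, age 65.**

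| Pre-dialysis Cr | Fall | Cr used | Man: eGFR, stage | Woman: eGFR, stage | Creatinine scheme (man / woman) |
|---|---|---|---|---|---|
| 5 | 50% | 2.5 | 21.5, G4 | 15.9, G4 | Severe/ESKD in both |
| 5 | 60% | 2.0 | 27.4, G4 | 20.3, G4 | Moderate in both |
| 5 | 70% | 1.5 | 37.6, G3b | 27.8, G4 | Moderate in both |
| 6 | 50% | 3.0 | 17.6, G4 | 13.0, G5 | Severe/ESKD in both |
| 6 | 60% | 2.4 | 22.5, G4 | 16.6, G4 | Moderate / Severe/ESKD |
| 6 | 70% | 1.8 | 30.8, G3b | 22.7, G4 | Moderate in both |
| 8 | 50% | 4.0 | 12.8, G5 | 9.5, G5 | Severe/ESKD in both |
| 8 | 60% | 3.2 | 16.4, G4 | 12.1, G5 | Severe/ESKD in both |
| 8 | 70% | 2.4 | 22.5, G4 | 16.6, G4 | Moderate / Severe/ESKD |
| 10 | 60% | 4.0 | 12.8, G5 | 9.5, G5 | Severe/ESKD in both |
| 10 | 70% | 3.0 | 17.6, G4 | 13.0, G5 | Severe/ESKD in both |
| 12 | 70% | 3.6 | 14.4, G5 | 10.7, G5 | Severe/ESKD in both |

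At 10 with a 50% fall, and at 12 with a 50 or 60% fall, both sexes stay G5.

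**Step 3: fall needed to leave G5 at age 65.** From 8 mg/dL: 1 - 3.47/8 = 57% in a man and 1 - 2.63/8 = 67% in a woman. From 12 mg/dL: 1 - 3.47/12 = 71% and 1 - 2.63/12 = 78%. To leave Severe/ESKD from 8 mg/dL: 1 - 2.4/8 = 70% and 1 - 2.0/8 = 75%.

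So the error can occur, more readily in men and at lower pre-dialysis values, and less readily in the creatinine scheme. The table shows when it occurs. It does not show how often.

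**The case against.** The strongest objection is that the mechanism is conditional at every step. The value used must be low enough, and many lowered values still give G5. A reader might infer that the latest value is the post-dialysis one. The documents speak only of a laboratory test date, so two samples on one day could tie, and the plan does not say which is taken. This stands: the claim has to be that such a patient may be staged too low.

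The creatinine scheme merges severe disease and ESKD, so a shift from ESKD to severe cannot show there. That also stands, but it does not remove the problem. A man at 2.4 mg/dL or a woman at 2.0 is shown as Moderate.

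A reader might also infer that G4 and G5 are the smallest groups, or that the error differs between compounds. Both are plausible, but the documents give no stage counts and no prescribing figures for dialysis patients, so neither is relied on here.

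Parts of the objectives, measures and analysis text are blacked out, and a dialysis rule could sit there. The sponsor can settle this. Still, 9.3.3 and Annex 3, where the stage is defined, are readable and contain none.

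Lastly, codes would not find every dialysis patient. Sections 9.1 and 9.9 say that care at other institutions is not in the data, and Section 7 describes procedure coding in the context of the DPC system. This limits the remedy but is no reason to use no codes at all.

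**Conclusion.** The point holds as a conditional misclassification. Renal stage comes from one creatinine value for everyone, and a dialysis patient is staged as less severe than ESKD when that value is at or below about 3.5 mg/dL (man) or 2.6 mg/dL (woman) at age 65 in the eGFR scheme. In the creatinine scheme the limits are 2.4 and 2.0 mg/dL. These thresholds follow from the plan alone. The creatinine values in dialysis patients are assumptions, and the number of patients affected cannot be derived.

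The documents do not support the stronger reading that dialysis patients with lowered creatinine are, as a rule, placed in G4 or better. Nor does the point reach the readable primary results: the primary outcome is baseline characteristics, and renal impairment is reported there by diagnosis, which does not depend on creatinine. Only the stage-based drug and dose results are exposed. It is worth correcting before the analysis because the rule is wrong for an identifiable group and the correction is cheap.

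**What to change.** In 9.3.3 and Annex 3:

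- Among patients with a creatinine result in the window, classify those with a maintenance-dialysis procedure code or related ICD-10 code in the look-back as *G5, dialysis* (Severe/ESKD in the creatinine scheme), whatever the creatinine value. Report them in a separate row.
- Show coded dialysis patients without a creatinine result separately, outside the stage distribution. Section 9.9 puts laboratory coverage at 350,000/2,600,000 = 13.5%. If coverage is similar in dialysis patients (an assumption), drawing them from all patients while G1-G4 come only from those with laboratory data would inflate their count about 1/0.135 = 7.4-fold relative to the other stages.
- State as a limitation that dialysis given at other institutions is missed, and confirm that outpatient claims carry the relevant codes.
- Reconcile the creatinine window. Section 9.3.3 allows 6 months, while 9.1 and 9.9 refer to the latest result 30 days before index. The rule above needs one window.

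The cost is a small code list, one assignment rule and a split G5 row. Capture of dialysis patients will remain incomplete.
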